1.3 Rationale

There are reasonably good data on liver tolerance to radiation therapy with conventional external beam therapy,^{4, 5} and there are some data on the use of high dose per fraction radiation therapy for patients with liver metastases. However, the location of the tumor in these studies has not been well defined and good data do not exist on radiation tolerance⁸ in the context of pre-existing cirrhosis or using the high doses per fraction that are used with stereotactic radiation therapy such as with the CyberKnife for centrally located tumors. There are also minimal dose-local control data for HCC either with conventional radiation therapy or with high dose per fraction stereotactic radiation therapy⁹⁻¹³. This proposal, using existing data from conventional radiation therapy as a base line, would help define these tolerance doses and also provide preliminary tumor control data¹⁴.

Since the time this protocol was initially written additional information has become available that allows us to estimate better the tolerance of the normal liver to high dose radiation therapy delivered in a small number of fractions. Much of these data are summarized in the QUANTEC analysis that was published in 2010¹⁵. This group has come out with formal recommendations for liver stereotactic radiation therapy as delivered here, based on the tolerance of normal liver. Most of these data are obtained with peripheral hepatic irradiation, so the question being asked in this protocol of tolerance of the portal structures (as well as of the hepatic parenchyma) is still a critically important issue. However, the overall tolerance of the hepatic parenchyma is less of a question for the patients with good pre-existing liver function. The data for the patients with poor baseline liver function is less well known, but should also build on the data for the patients with good function.

2.0 STUDY OBJECTIVES

2.1 Primary Objective

To determine a tolerable dose of radiation delivered by the CyberKnife in two cohorts of patients who have hepatocellular carcinoma or liver metastases from colorectal cancer or other tumors:

Cohort 1: Patients with good liver function as defined by, no more than Child-Pugh Class A if cirrhosis is present and disease limited to peripheral lesions

Cohort 2: Patients with compromised liver function as defined by patients with Child-Pugh Class B.

2.2 Secondary Objectives

To develop preliminary data on local response/control of HCC, colorectal liver metastases, and liver metastases from other primary sites to these radiation doses.

3.0 TREATMENT PLAN

3.1 Schema

After initial evaluation for eligibility and signing of the informed consent, fiducial markers will be placed via percutaneous approach by interventional radiology.

CT scans will be obtained, and when necessary, CT scans will be registered with MRI scans. The gross tumor volume (GTV) as well as the location of the GTV will be defined based on placement of the fiducial markers. The fiducial placement will be carried out by interventional radiology. For treatment planning, the GTV will be expanded by 5 mm in all directions except for supero-inferior where the expansion will be 8 mm. This expansion will account for both clinical target volume (CTV) expansion and motion. Treatment planning software will be used to plan radiation delivery schemes that will best meet the dose criteria defined above. The prescription dose will be modified as necessary as per section 3.3 to meet the defined liver tolerance dose.

Because of the difference in anatomy and expected normal tissue tolerance based on hepatic function, there are two well defined patient cohorts. The first cohort comprises of patients with good liver functions and peripheral lesions. The second cohort is comprised of patients with Child-Pugh Class B lesions where liver tolerance is more likely to be a problem.

Treatments will be delivered with standard CyberKnife procedures and the Synchrony™ option to account for respiratory motion and set up variations. The fiducial location will be the prime determinant of the delivery site and respiratory motion.

3.2. Treatment Dosage and Administration

Fiducial placement:

Standard techniques will be used as for biopsy, but gold seed markers compliant with the CyberKnife software will be placed in the vicinity (within 6 cm) of the tumor. At least 3, but generally 4-5, markers will be placed in such a manner as to not be co-linear, and as widely spaced as possible. Markers can be placed within the tumor mass, but some of the markers should be placed in the normal liver surrounding the tumor. It is recommended that at least 1 gold fiducial should be implanted inside the gross tumor. The fiducials may be placed via percutaneous needle placement under imaged guidance and local anesthesia or utilizing endoscopic ultrasound techniques in the standard fashion. Similar to fine needle biopsy, it is possible that placement of the fiducials may result in inflammation, bleeding, infection, pneumothorax or bile leak.

Immobilization Cradle and Treatment Planning CT Imaging

At least 6 days after fiducial placement (to enable resolution of any injury that may have occurred during fiducial placement and to allow for fiducial stabilization), subjects will return to the Radiation Oncology Clinic. If fiducials have been placed surgically, then the planning CT should be done as soon after 6 days as deemed clinically appropriate.

Prior to or at this visit, a radiation therapy immobilization device (i.e. Alpha Cradle) will be custom made for each subject to position them during the treatment.

While positioned in the immobilization device, a treatment planning CT scan with and without IV contrast will be taken. Patients with allergies to the contrast agent will be premedicated per institutional protocol. The CT scans taken for treatment planning will be taken with a breath hold with the tumor located approximately midway axially of the slices required. This imaging set will be downloaded to the CyberKnife treatment planning system to develop the radiosurgery treatment plan.

A radiosurgical treatment plan will be developed based on tumor geometry and proximity to vital structures. The treating surgeon and or the treating radiation oncologist will contour the tumor as well as all dose-limiting structures. Briefly, the lesion representing the gross tumor volume (GTV) will be outlined on sequential axial computed tomography images utilizing soft tissue/liver windowing. Planning target volume (PTV) is created by expanding GTV by 0.5-0.8 cm in all directions. The dose will be prescribed to the minimal isodose line that covers (>95%) the PTV. All vital structures close to the irradiated target, potentially including the heart, esophagus, aorta, spinal cord, and stomach will be contoured for the purpose of limiting incidental radiation to these structures and for the development of dose volume histograms (DVH).

The Stereotactic Radiosurgical Procedure

The CyberKnife (CK) treatment will generally be initiated within 1 to 2 weeks of the planning treatment CT. On the day of CK treatment, the subject will be taken into the CK treatment room and the applicable LED (light emitting diode) monitors will be attached. The LEDs will assist the system to track the tumor throughout the respiratory cycle. The subject then will be set up in their immobilization cradle on the CyberKnife couch. X-rays will be taken with the CyberKnife System to ensure that the tumor is aligned in a manner consistent with the position in which the treatment plan CT image was taken. Fiducial locations in the images will be extracted and compared to the fiducial locations in the CT scans to estimate tumor movements. Once the tumor is properly aligned, SRS will be initiated. During the course of SRS, x-rays will continue to be taken periodically to ensure correct tumor alignment. The SRS treatment will be administered in three to five fractions, given over 3-15 days.

First Cohort (good liver function):

The planned initial dose to all patients with peripheral lesions and no more than Child-Pugh Class A will be 1500 cGy delivered to the prescription point for 3 fractions for a total of 4500 cGy if the dose-normal tissue constraints as defined below can be met. Treatments are delivered

≥ 48 hrs apart and should be completed within 2 weeks depending on routine scheduling or maintenance related issues with the CyberKnife. No treatment should be completed in less than 5 days (i.e., M, W, F is most common).

Second Cohort (compromised liver function):

The planned initial dose delivered to all patients with Child-Pugh Class B will be 700 cGy delivered to the prescription point for 5 fractions for a total of 3500 cGy if the dose-normal tissue constraints defined below can be met. Treatments will generally be given over approximately 2 weeks with ≥ 48 hrs between the fractions.

For both cohorts, the dose will generally be quoted at the 70-80% isodose line and this should encompass the entire planning target volume (PTV). Higher isodose lines can be used for prescription purposes if that isodose line encompasses the PTV. Lower isodose lines should not be used if the fields can be modified appropriately. If lower isodose lines are required, they should not be less than 60%. The 100% isodose line is defined as the maximum dose in the tumor.

Dose-Volume Constraints- Liver Tolerance Parameters**i). First Cohort: Good liver function (as defined in primary objective) and peripheral lesions:**

Full radiation doses will be used if the dose to 35% of the liver can be kept below a total dose of 1500 cGy, the dose to 50% of one kidney can be kept below 1400 cGy, and/or the maximum point dose to the spinal cord can be kept to ≤ 1500 cGy. In addition, the total volume of liver kept below 1500 cGy should be at least 700 cm³. If these normal tissue dose constraints cannot be met, then the dose/fraction should be lowered by a 250 cGy increment to meet this dose constraint (i.e., 1250 x 3, 1000 x 3). Tumor size per se will not be a factor that will affect radiation dose, although it will affect the ability to meet the liver tolerance parameter. Tumor volumes will be recorded based on diagnostic imaging studies. Attempts will be made to minimize the dose to 35% of the liver, and not just meet the dose constraint. If dose constraints cannot be met after two decrements in dose per fraction as described above, the patient will not be eligible for study. See Tables 1 and 2..

Maximum dose to greater than 1 cc of the esophagus, heart, stomach, and small bowel (including duodenum) must be kept below a total of 3000 cGy. The maximum dose to greater than 1 cc of the rib and chest wall must be kept below 4000 cGy. The prescription dose will be decreased in 250 cGy per fraction increments to meet this constraint.

ii). Second Cohort: Compromised liver function (as defined in primary objective):

Full radiation doses will be used if the dose to 50% of the liver can be kept below a total dose of 1500 cGy, the dose to 50% of one kidney can be kept below 1400 cGy, and/or the maximum point dose to the spinal cord can be kept to ≤ 1500 cGy. In addition, the total volume of liver kept below 1500 cGy should be at least 700 cm³. If these normal tissue dose constraints cannot be met, then the dose/fraction should be lowered by 150 cGy increments to meet this dose constraint (i.e., 550 x 5, then 400 x 5). Tumor size per se will not be a factor that will affect

radiation dose, although it will affect the ability to meet the liver tolerance parameter. Tumor volumes will be recorded based on diagnostic imaging studies. Attempts will be made to minimize the dose to 35-50% of the liver, and not just maintain the dose constraint. If dose constraints cannot be met after two decrements in dose per fraction as described above, the patient will not be eligible for study. The expectation is that patients with Child-Pugh Class B will have lower doses because of these dose constraints. See Tables 1 and 2. The target mean liver dose in this cohort is ≤ 1300 cGy.

Maximum dose to greater than 1 cc of the esophagus, heart, stomach, and small bowel (including duodenum) must be kept below a total of 3000 cGy. The maximum dose to greater than 1 cc of the rib and chest wall must be kept below 4000 cGy. The prescription dose will be decreased in 150 cGy per fraction increments to meet this constraint. Fractional dose reduction for both cohorts will be carried out as described in the following table:

Table 1: Fractional Dose Reduction Criteria

Max of Single Liver Lesion	Number of Fractions	Fractional Dose	Total Dose	Constraints and Fractional Dose Reduction ¹
Cohort 1 (Good liver function)	3	15 Gy	45 Gy	
Reduce fractional dose by 250cGy until all the following 5 parameters have been met:
 
 1. V_{15} of liver is < 35% of liver 2. 700cc of liver < 15 Gy 3. Max dose to > 1 cc of esophagus, heart, stomach, small bowel < 30 Gy, and max dose to >1 cc of rib and chest wall <40 Gy 4. 50% of one kidney <14 Gy 5. Max point dose to spinal cord of 15 Gy
Cohort 2 (Compromised liver function)	5	7Gy	35 Gy	
Reduce fractional dose by 150cGy until all the following parameters have been met:
 
 1. V_{15} of liver is < 50% of liver 2. 700cc of liver < 15Gy 3. Max dose to > 1 cc of esophagus, heart, stomach, small bowel < 30 Gy, and max dose to >1 cc of rib and chest wall <40 Gy 4. 50% of one kidney <14 Gy 5. Max point dose to spinal cord of 15 Gy

¹ If the dose constraints cannot be achieved with two dose reductions (e.g., 15 Gy reduced to 10 Gy fraction still results in 700 cc of liver receiving >15 Gy for Cohort 1) then the patient is not evaluable for toxicity or local control, and should be removed from the study.

Table 2: Dose Levels by Cohort

Max of single Liver lesion	Number of Fractions	Fractional Dose	Number of subject	Total Dose	Constraints and Fractional Dose Reduction ²
Cohort 1 ¹ (Good liver function)	3	Dose Level -2: 10.0 Gy Dose level -1: 12.5 Gy Dose level 1: 15 Gy Dose level 2: 17.5 Gy Dose level 3: 20.0 Gy	10 10 10 10 10	Dose Level -2: 30.0 Gy Dose level-1: 37.5Gy Dose Level 1: 45 Gy Dose Level 2 52.5 Gy Dose Level 3: 60.0 Gy	Reduce fractional dose by 250cGy until all the following 5 parameters have been met: 1. V ₁₅ of liver is < 35% of liver 2. 700cc of liver < 15 Gy 3. Max dose to > 1 cc of esophagus, heart, stomach, small bowel < 30 Gy, and max dose to >1 cc of rib and chest wall <40 Gy 4. 50% of one kidney < 14 Gy 5. Max point dose to spinal cord of 15 Gy
Cohort 2 ¹ (Compromised liver function)	5	Dose Level -2: 4.0 Gy Dose Level-1: 5.5 Gy Dose Level 1: 7 Gy Dose Level 2: 8.5 Gy Dose Level 3: 10 Gy	10 10 10 10 10	Dose Level -2 20.0 Gy Dose Level-1: 27.5 Gy Dose Level 1: 35 Gy Dose Level 2: 42.5 Gy Dose Level 3: 50 Gy	Reduce fractional dose by 150cGy until all the following parameters have been met: 1. V ₁₅ of liver is < 50% of liver 2. 700cc of liver < 15 Gy 3. Max dose to > 1 cc of esophagus, heart, stomach, small bowel < 30 Gy, and max dose to >1 cc of rib and chest wall <40 Gy 4. 50% of one kidney < 14 Gy 5. Max point dose to spinal cord of 15 Gy

¹ Escalation of the two cohorts will be done separately as their tolerance might be substantially different. No intra-patient dose escalation is allowed.

² If the dose constraints cannot be achieved with two dose reductions (e.g., 15 Gy reduced to 10 Gy fraction still results in 700 cc of liver not receiving < 15 Gy) then the patient is not evaluable for toxicity or local control, and should be removed from the study.

* Escalation of the two cohorts will be done separately as their tolerance might be substantially different.

Table 2 displays dose levels considered for the study.

1). The primary end-point will be the development of radiation induced liver disease as measured by the > 2-fold worsening of liver functional parameters, clinically apparent worsening of portal hypertension, new or worsening bleeding esophageal varices, or worsening ascites within the first 3 months from initiation of treatment. These will be considered dose-limiting hepatic toxicities. Increases in hepatic enzymes by less than 2-fold alone will not be considered a dose-limiting radiation induced hepatic toxicity if they are not accompanied by other signs of deteriorating liver function as any irradiation of normal liver would be expected to elevate enzymes.

The two patient cohorts will be evaluated separately for determination of toxicity. Deteriorating liver function that can be explained by tumor progression or other non-treatment related events will not be considered a treatment toxicity for the purpose of this analysis.

A dose level will be considered beyond tolerance depending on the fraction of patients who experience a dose-limiting radiation induced hepatic toxicity. See Table 3. Once this happens, enrollment to that dose level will be halted. If this happens at dose level 1, subsequent patients eligible for full dose therapy will enroll into dose level -1. If dose level -1 is found intolerable in patients eligible for full dose therapy, the trial will be stopped.

Patients will also be evaluated for other unexpected toxicities according to the NCI CTCAE, Version 3.0. Unexpected Grade 3 toxicities thought to be due to therapy will be scored as 1 and unexpected Grade 4 toxicities thought to be due to therapy will be scored as 2. A patient with both unexpected Grade 3 and Grade 4 toxicities will be counted as a patient with unexpected Grade 4 toxicity. If the total score exceeds 3 in the first 3, 4, or 5 patients, or exceeds 4 at any point within a dose level, enrollment to that dose level will be halted and that dose will be considered beyond tolerance. See Table 4. If this happens at dose level 1, subsequent patients eligible for full dose therapy will enroll into dose level -1. If dose level -1 is found intolerable in patients eligible for full dose therapy, the trial will be stopped.

Table 3:

# of patients with a DLT	Total # patients in cohort	Action
≥3	3, 4, 5	Stop dose-cohort ¹
≥4	6, 7, 8, 9, 10	Stop dose-cohort ¹

¹If this occurs within Dose level 1, enter the next group of patients eligible for full dose to Dose level -1. If dose level -1 is found intolerable in patients eligible for full dose therapy, the trial will be stopped.

Table 4:

# of patients with unexpected Grade 3 ¹	# of patients with unexpected Grade 4	Total # patients in cohort	Action
≥0	≥2	3, 4, 5	Stop dose-cohort ²
≥4	≥0		
≥0	≥3	6, 7, 8, 9, 10	Stop dose-cohort ²
≥1	≥2		
≥5	≥0		

¹A patient with both unexpected Grade 3 and Grade 4 toxicities is counted as a patient with unexpected Grade 4 toxicity

²If this occurs within Dose level 1, enter the next group of patients eligible for full dose to Dose level -1. If patients eligible for full dose cannot tolerate dose level -1, the trial will be stopped.

The development of any Gr. 5 toxicity thought related to therapy will result in temporary suspension of the trial for full evaluation. If specific toxicity related to an irradiated organ is found, alteration of the dose parameters for that tissue will be modified, although not necessarily a reduction in the planned tumor dose.

2). The secondary study end-point will be local tumor response and control. Our expectation is that a dose of 1500 cGy per fraction for 3 fractions (4500 cGy total) will be adequate for control of irradiated lesions of moderate size, but higher doses may be needed. In the second cohort the optimal dose is less clear, and dose escalation will likely be desired. Patients will be evaluated for local control at 5-6 months after irradiation. A minimum of 10 patients will be entered onto each dose cohort. However, if there are 4 local failures within a cohort at dose level 1 dose escalation may proceed provided the tolerance parameters are acceptable (that is, conditions in both Tables 5A and 5B are satisfied), and patients have been evaluated for toxicity for at least 3 months from the initiation of therapy. At that point, dose escalation to a nominal prescription dose per fraction of 1750 cGy in the first cohort, and 850 cGy in the second cohort, will be undertaken. A second dose escalation with the same increase in dose/fraction could occur based on the same parameters as above. Escalation of the two cohorts will be done separately as their tolerance might be different. No intra-patient dose escalation will be allowed. For dose escalation, if the proposed dose for escalation is found to be too toxic, based on Tables 3 and 4, the study will be stopped. All patients in a cohort will be followed for 3 months from the time of initiation of therapy for evaluation of toxicity, prior to dose escalation in each cohort.

Table 5A

# of patients with a DLT	Total # patients in cohort	Action
0	5, 6, 7, 8	DLT rate warrants escalation to next dose level for subsequent patients ¹
≤ 1	9, 10	DLT rate warrants escalation to next dose level for subsequent patients ¹

¹ Dose escalation will only occur in patients eligible for full dose, see text of protocol

Table 5B

# of patients with unexpected Grade 3 ¹	# of patients with unexpected Grade 4	Total # patients in cohort	Action
≤ 1	0	5, 6, 7, 8	Rate of unexpected toxicities warrants escalation
≤ 2	0	9, 10	Rate of unexpected toxicities warrants escalation
≤ 0	1		

¹ A patient with both unexpected Grade 3 and Grade 4 toxicities is counted as a patient with unexpected Grade 4 toxicity

To summarize, the goal is to find a dose such that:

- 1). The rate of dose limiting hepatic toxicity at that dose does not exceed 0.33.
- 2). The rate of unexpected Grade 3 plus double the rate of Grade 4 toxicities does not exceed 0.4.;
- 3). The rate of the local tumor control at that dose is at least 70%.

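### Section 3.2 joins the liver, kidney and cord limits for full dose with *and/or*, while Tables 1 and 2 require every limit to be met; the text should say *and* in both cohorts.

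*Combined protocol and SAP*

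**What the plan says.** In Section 3.2, under Dose-Volume Constraints, the first-cohort paragraph sets three conditions for full dose: less than 15 Gy to 35% of the liver, less than 14 Gy to half of one kidney, "and/or the maximum point dose to the spinal cord can be kept to ≤ 1500 cGy". The second-cohort paragraph has the same structure with 50% of the liver in place of 35%; its kidney and cord clause reads "the dose to 50% of one kidney can be kept below 1400 cGy, and/or the maximum point dose to the spinal cord". A separate sentence in each paragraph adds that "the total volume of liver kept below 1500 cGy should be at least 700" cm³.

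Tables 1 and 2 state the rule differently. For cohort 1: "Reduce fractional dose by 250cGy until all the following 5 parameters have been met". For cohort 2: "Reduce fractional dose by 150cGy until all the following parameters have been met". Each list has five items: the liver percentage, the 700 cc liver volume, the limits for hollow organs, heart and chest wall, the kidney limit and the cord limit.

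Other text in Section 3.2 supports the tables. The cohort 1 starting dose is given "for a total of 4500 cGy if the dose-normal tissue constraints as defined below can be met", with an equivalent condition for cohort 2. The cohort 1 paragraph continues "If these normal tissue dose constraints cannot be met, then the dose/fraction should be lowered by a 250 cGy increment", and cohort 2 has the same rule with 150 cGy steps. Table 1 is introduced with "Fractional dose reduction for both cohorts will be carried out as described in the following table".

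**The concern.** The text and the tables state the same dose-assignment rule, and they differ on whether one limit may fail. These are normal-tissue safety limits, and Section 6.4 describes a multi-center study, so sites outside the coordinating center have to apply the sentence as written.

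Kidney and cord are the most exposed, because no other listed parameter covers them. Inclusion criterion 8 speaks of hepatic tolerance, and exclusion criteria 10 and 11 of the liver constraint, so neither clearly closes the gap.

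Full-dose status also feeds the dose-finding rules. If level 1 is intolerable, later patients who qualify for full dose go to level -1, and the footnote to Table 5A restricts escalation to such patients. A loose definition could therefore change who is placed at a level, although the boundaries themselves stay the same.

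**Working it through.** **Step 1: compare the numerical limits.** Inputs are the two cohort paragraphs of Section 3.2 and Tables 1 and 2.

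| Limit | Text | Tables 1 and 2 |
|---|---|---|
| Liver, cohort 1 | 35% below 1500 cGy | V15 < 35% |
| Liver, cohort 2 | 50% below 1500 cGy | V15 < 50% |
| Kidney | 50% of one below 1400 cGy | 50% of one < 14 Gy |
| Cord, maximum point | ≤ 1500 cGy | 15 Gy |
| Connective | *and/or* | all |

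The numbers agree. On these three limits the connective is the only conflict.

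**Step 2: compare the two readings.** Three pass/fail limits give 2³ = 8 combinations. Under *and*, full dose is allowed in 1 of 8 (all met). Under *or*, it is allowed in 7 of 8 (all except none met). The readings disagree in 7 − 1 = 6 combinations, those with one or two limits failed. This counts logical outcomes and is not an estimate of how often they occur.

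**Step 3: dose consequence.** From Table 2, one step is:
- cohort 1: 3 × 2.5 Gy = 7.5 Gy (45 − 37.5);
- cohort 2: 5 × 1.5 Gy = 7.5 Gy (35 − 27.5).

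A patient wrongly kept at level 1 receives at least this much more than the tables allow. If two reductions were needed, the excess is 15 Gy (45 − 30, or 35 − 20).

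**Step 4: how far the 700 cm³ rule protects the liver limit.** This rule stands outside the *and/or* list. If it is met, then for liver volume L in cm³

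V15 ≤ 1 − 700/L.

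The percentage limit f is then met automatically when 1 − 700/L < f, that is, when L < 700/(1 − f):
- cohort 1: 700/0.65 = 1076.9 cm³;
- cohort 2: 700/0.50 = 1400 cm³.

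The loose wording can affect the liver limit only at or above those volumes. The documents give no liver volumes, so the range below is an assumption.

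| Assumed L (cm³) | Largest V15 with exactly 700 cm³ spared | Cohort 1 limit (35%) | Cohort 2 limit (50%) |
|---|---|---|---|
| 1200 | 1 − 700/1200 = 41.7% | can be exceeded | protected |
| 1500 | 1 − 700/1500 = 53.3% | can be exceeded | can be exceeded |
| 2000 | 1 − 700/2000 = 65.0% | can be exceeded | can be exceeded |

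**The case against.** The strongest reply is that Section 3.2 settles the matter itself. It makes Table 1 govern dose reduction, and Table 1 demands every parameter. The sentences after the *and/or* list treat the limits together, lower the dose if they fail, exclude the patient if two reductions are not enough, and cite both tables. *And/or* also admits the *and* reading, so one may call the sentence ambiguous rather than contradictory. A planner who follows the whole section should reach the right rule.

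Most of that stands, and it is why the point is minor. Three further cautions also stand. The 7-in-8 against 1-in-8 count says nothing about frequency. The 7.5 Gy figure is conditional on a misreading of unknown probability. The liver-volume range is assumed and does not address kidney or cord.

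What does not follow is that the wording can be left. A permissive reading of a safety limit remains in the operative sentence of both cohorts, and the reader has to override it from elsewhere. The summary of Amendment 1, taken only as a sign of intent, says this text was expanded to carry every constraint in Table 1. The correction fits that aim.

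**Conclusion.** The text is wrong as written, at low severity. The tables and the neighbouring sentences show that all limits are meant to apply, so the likely practical effect is limited. If the sentence were misapplied, the patient would receive at least 7.5 Gy above the dose the tables allow, in either cohort. No frequency can be derived from the documents.

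Kidney and cord carry most of the exposure. The liver percentage is exposed only from about 1077 cm³ of liver in cohort 1 and 1400 cm³ in cohort 2, given that the 700 cm³ rule is enforced. Sample size and the stopping and escalation boundaries in Tables 3, 4, 5A and 5B are unaffected.

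**What to change.** In both cohort paragraphs of Section 3.2, replace *and/or* with *and*. Then add one sentence: *Full dose requires that every parameter listed for the cohort in Tables 1 and 2 is met.* Naming both tables is tidier than naming Table 1 alone: the parameters are identical, but Table 1 shows only the level 1 doses, while Table 2 covers the escalated levels as well.

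The cost is one connective in each of two paragraphs and one added sentence. No numerical limit or dose level has to change.
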